8.2.3 Vital signs

The vital signs include tympanic temperature, systolic and diastolic BP, pulse rate and respiratory rate and will be assessed as outlined in the SoA, [Table 1](#).

Blood pressure should be measured before the HD procedure when applicable. For patients on PD, BP should be measured in the morning prior to the patient performing the first exchange of the day. Blood pressure and pulse rate should be measured with a completely automated device in triplicate with at least 1-minute intervals between measurements after being comfortably at rest in a seated position with the back and feet supported (ie, by chair back and floor or platform, respectively) quietly for at least 5 minutes. Manual techniques will be used only if an automated device is not available. The position of the patient should be comfortable with the arm where the BP is recorded to be within the level of heart (the middle of the cuff on the upper arm is at the level of the right atrium [the midpoint of the sternum]). The patient will be instructed to relax as much as possible and to not talk during the measurement procedure. The same device should preferably be used for the patient during the course of the study and in the same arm. The first reading of the BP and pulse rate should be

rejected. The second and third readings should be averaged to give the measurement to be recorded in the eCRF.

8.2.4 Electrocardiograms

A 12-lead electrocardiogram (ECG) measurement will be obtained at screening as outlined in the SoA, [Table 1](#), using an ECG machine that automatically calculates the pulse rate and measures PR, QRS, QT, and QTc intervals.

8.3 Collection of adverse events

The Investigator is responsible for ensuring that all staff involved in the study are familiar with the content of this section.

The definitions of an AE or SAE can be found in [Appendix B](#).

Adverse events will be reported by the patient (or, when appropriate, by a caregiver, surrogate, or the patient's legally authorized representative).

The Investigator and any designees are responsible for detecting, documenting, and recording events that meet the definition of an AE or SAE. For information on how to follow/up AEs see Section [8.3.3](#).

8.3.1 Method of detecting adverse events and serious adverse events

Care will be taken not to introduce bias when detecting AEs and/or SAEs. Open-ended and non-leading verbal questioning of the patient is the preferred method to inquire about AE occurrences.

8.3.1.1 Reporting of AEs/SAEs in relation to COVID-19

All AEs/SAEs should be reported in line with instructions for safety reporting documented in the CSP.

For patients experiencing signs and symptoms indicating an infection, an attempt will be made to determine whether the COVID-19 virus is the infectious organism and the AE will be recorded accordingly. If a patient presents with clinical signs and symptoms suggestive of COVID-19, a test will be requested where possible:

- If the test is positive, record “COVID-19 positive” in the Adverse Event Field.
- If the test is negative, record “COVID-19 negative” in the Adverse Event Field, along with the AE/SAE signs and symptoms and/or other diagnosis.

If a test has not been performed or result is not available and signs and symptoms, as judged by the Investigator, are suggestive of COVID-19 infection, record “COVID-19 suspected” in

the Adverse Event Field. If the Investigator has other concurrent diagnoses for the patient's signs and symptoms (eg, pneumonia), these will be recorded as separate AEs.

8.3.2 Time period and frequency for collecting adverse event and serious adverse event information

All AEs and SAEs will be collected from the time of signature of informed consent throughout the Treatment Period and including the Follow-up Period.

All SAEs will be recorded and reported to the Sponsor or designee within 24 hours, as indicated in [Appendix B](#). The Investigator will submit any updated SAE data to the Sponsor or designee within 24 hours of it being available.

All roxadustat Adverse Drug Reactions (ie, AEs that the Investigator considers that there is a reasonable possibility that the AE may have been caused by roxadustat) will be reported to the Sponsor or designee within 24 hours.

Investigators are not obligated to actively seek AE or SAE information in study patients who are no longer on the study. However, if the Investigator learns of any SAE, including a death, at any time after a patient's last visit and he/she considers the event to be reasonably related to the study treatment or study participation, the Investigator should notify the Sponsor.

The method of recording, evaluating, and assessing causality of AE and SAE and the procedures for completing and transmitting SAE reports are provided in [Appendix B](#).

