8.3.7 Adverse events based on examinations and tests

The results from the CSP-mandated laboratory tests and vital signs will be summarized in the Clinical Study Report (CSR).

The Investigator should make an assessment of the available laboratory results with regard to clinically relevant abnormalities and should determine if any of the laboratory values are clinically significant. The laboratory results should be signed and dated and retained at study site as source data for laboratory variables.

Any protocol-mandated laboratory values or vital signs from the baseline visit that the Investigator assesses to be clinically significant, should be reported in the medical history. Deterioration as compared to baseline of any protocol-mandated laboratory values or vital signs that the Investigator assesses to be clinically significant should be reported as AEs. If deterioration of a laboratory value or vital sign meets the seriousness criteria, it should be reported as an SAE. If the reason for discontinuation of study treatment is due to deterioration of a laboratory value or vital sign compared to baseline (whether or not considered clinically significant), this should be reported as an AE. If a laboratory value or vital sign is outside the normal range, and the Investigator has assessed it as not clinically significant and study treatment has not been discontinued as a result of the laboratory value or vital sign, this does not need to be reported as an AE.

If deterioration in a laboratory value/vital sign is associated with clinical signs and symptoms, the sign or symptom will be reported as an AE and the associated laboratory result/vital sign will be considered as additional information. Wherever possible, the reporting Investigator uses the clinical, rather than the laboratory term (eg, anemia versus low Hb value). In the absence of clinical signs or symptoms, clinically relevant deteriorations in non-mandated parameters should be reported as AE(s).

Deterioration of a laboratory value, which is unequivocally due to disease progression, should not be reported as an AE/SAE.

Any new or aggravated clinically relevant abnormal medical finding as compared with the baseline assessment will be reported as an AE unless unequivocally related to the disease-under study (DUS), see Sections 8.3.9 and 8.3.10.

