9.4.4 Safety analyses

All safety analyses will be performed on the safety analysis set and will be analyzed descriptively.

Adverse events (and also separately SAEs) will be summarized by study treatment group by incidence summaries by Medical Dictionary for Regulatory Activities (MedDRA) System Organ Class (SOC) and Preferred Term (PT).

Laboratory data for hematology, clinical chemistry and liver function test will be summarized by visit and study treatment group.

Vital signs will be summarized by visit and study treatment group.

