Appendix B Adverse Event Definitions and Additional Safety Information

B 1 Definition of adverse events

An adverse event (AE) is the development of an undesirable medical condition or the deterioration of a pre-existing medical condition following or during exposure to a pharmaceutical product, whether or not considered causally related to the product. An undesirable medical condition can be symptoms (eg, nausea, chest pain), signs (eg, tachycardia, enlarged liver) or the abnormal results of an investigation (eg, laboratory findings, electrocardiogram [ECG]). In clinical studies, an AE can include an undesirable medical condition occurring at any time, including run-in or washout periods, even if no study treatment has been administered.

B 2 Definitions of serious adverse event

A serious adverse event (SAE) is an AE occurring during any study phase (ie, screening, run-in, treatment, follow-up) and fulfils one or more of the following criteria:

- Results in death
- Is immediately life-threatening
- Requires in-patient hospitalization or prolongation of existing hospitalization
- Results in persistent or significant disability or incapacity
- Is a congenital abnormality or birth defect
- Is an important medical event that may jeopardize the patient or may require medical intervention to prevent one of the outcomes listed above

Adverse Events for malignant tumours reported during a study should generally be assessed as SAEs. If no other seriousness criteria apply, the ‘Important Medical Event’ criterion should be used. In certain situations, however, medical judgement on an individual event basis should be applied to clarify that the malignant tumour event should be assessed and reported as a non-serious AE. For example, if the tumour is included as medical history and progression occurs during the study, but the progression does not change treatment and/or prognosis of the malignant tumour, the AE may not fulfil the attributes for being assessed as serious, although reporting of the progression of the malignant tumour as an AE is valid and should occur. Also, some types of malignant tumours, which do not spread remotely after a routine treatment that does not require hospitalization, may be assessed as non-serious; examples include Stage 1 basal cell carcinoma and Stage 1A1 cervical cancer removed via cone biopsy.

B 3 Definition of adverse drug reactions

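### Section 8.3.1.1 puts COVID-19 test results in the Adverse Event Field, against the protocol's own AE rules, so event counts and SOC/PT rows can gain a non-event

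*Protocol*

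**What the plan says.** Section 8.3.1.1 sets the trigger: "If a patient presents with clinical signs and symptoms suggestive of COVID-19, a test will be requested where possible". What is then entered depends on the result.

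- **Negative:** "If the test is negative, record “COVID-19 negative” in the Adverse Event Field, along with the AE/SAE signs and symptoms and/or other diagnosis".
- **Positive:** 'COVID-19 positive' goes in the same field. This bullet does not ask for signs, symptoms or a diagnosis beside it.
- **No test or no result, with suggestive symptoms:** 'COVID-19 suspected' goes in the field.
- **Other concurrent diagnoses:** "these will be recorded as separate AEs".

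The subsection opens by saying that AEs follow the protocol's general safety reporting instructions. The relevant ones are:

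- **Section 8.3** has investigators record events that meet the AE or SAE definition.
- **Section 8.3.4** lists the verbatim event among the variables for every AE. A description of the event is listed only for SAEs, and no swab result is listed.
- **Section 8.3.6** prefers a diagnosis to a list of signs and symptoms.
- **Section 8.3.7** says: "Wherever possible, the reporting Investigator uses the clinical, rather than the laboratory term". Where a deteriorated value comes with symptoms, "the sign or symptom will be reported as an AE and the associated laboratory result/vital sign will be considered as additional information".
- **Appendix B 1** admits symptoms, signs or "the abnormal results of an investigation (eg, laboratory findings, electrocardiogram [ECG" (closing brackets omitted).

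Section 9.4.4 summarizes AEs descriptively, by treatment group, as incidence by MedDRA SOC and PT.

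**The concern.** The general rules and the COVID-19 bullets tell sites different things about what names an event. Under the general rules, a patient with cough and a negative swab has one AE, cough. Under the bullet, the same field also receives a normal test result.

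The verbatim term is the only event-naming variable collected for every AE, and the SOC and PT summaries are built from AE terms. A result entered there can therefore reach the tables unless something later removes it, and the protocol does not say what would. Approximately 7 to 10 sites are planned. Some may enter a separate line; others may write a combined string that mixes the result with the symptom.

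At stake is the accuracy of event counts and individual rows in the safety tables of a small trial, where a single patient is visible. The primary endpoint, its significance level and its power are not involved.

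**Working it through.** The protocol states no AE rate, count or threshold on this point, so there is no figure to reproduce. The check compares the texts and then bounds the possible effect.

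**1. Is a negative swab an AE under the protocol's definition?** No. Appendix B 1 admits an investigation result only if it is abnormal. Table 4 lists the swab among the laboratory variables. Section 8.3.7 does not require an AE report even for an out-of-range value that is judged not clinically significant and has not led to stopping study treatment. A normal result falls further short.

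**2. Is a positive result the right name for an event?** Not under Sections 8.3.6 and 8.3.7. The first prefers the diagnosis and the second the clinical term. 'COVID-19 positive' is a test outcome; the illness is the event.

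**3. Does the opening reference to the general instructions resolve the conflict?** No. The bullets say specifically what to write in the field, and what they say departs from those instructions.

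**4. Effect on the proportion of patients with any AE.** The bullet applies only to patients with suggestive signs and symptoms, and the entry is made beside the AE signs, symptoms or diagnosis. The patient already counts once. Change: 0.

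**5. Effect on event counts and on an SOC/PT row.** Inputs:

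- Randomized: 20 to 60 patients, 1:1 (Sections 4.1.2 and 6.3), so about 20/2 = 10 to 60/2 = 30 per arm.
- Safety analysis set: randomized patients with at least one dose (Section 9.3). The first dose is given at the site after randomization on Day 1 (Section 4.1.1), so this set should be close to the number randomized.

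If an entry is coded as its own term, and a patient has one such entry, that patient adds 1 event and 1/n to the row:

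- n = 10 per arm: 1/10 = 10.0 percentage points.
- n = 30 per arm: 1/30 = 3.3 percentage points.

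**6. Total effect.** This would be the number of affected patients multiplied by the per-patient figure. The protocol does not give that number, so the total cannot be calculated.

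**The case against.** The strongest defence is that the negative result only qualifies a real AE. The bullet applies to symptomatic patients, joins the result to the symptoms or diagnosis, and never calls the result a separate AE; that wording is kept for other concurrent diagnoses. Read with Appendix B 1 and Section 8.3.7, cough is the event and the swab result is background. Coding conventions, which could remove the qualifier, normally sit in data-management documents that are not shown.

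Part of this stands. A spurious row is a possibility that depends on data entry and coding, not a certainty. The symptom-first rule in Section 8.3.7 is also written for deteriorated values, so it reaches a negative swab by analogy. Neither point removes the contradiction: the instruction still names the Adverse Event Field, and the listed variables for a non-serious AE give the result no other place.

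A reader might infer more than the protocol supports:

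- **That overall AE incidence is miscounted.** It is not, because the affected patient already has an AE.
- **That infections will be coded away from infection terms.** The protocol does not say how 'COVID-19 positive' would be coded, and Section 8.3.1.1 aims to establish whether the virus is the infecting organism.
- **That the arms will differ because the trial is open-label.** Section 4.1.1 leaves testing after a pre-visit or patient-initiated contact to the investigator's discretion. Section 8.3.1.1, however, asks for a test wherever possible, and untested suggestive cases also receive a COVID-19 entry. A difference is conceivable but not shown.
- **That one patient moves a row by 1/8 = 12.5 points, or two by 2/8 = 25.** Eight per arm is the lower end of the synopsis figure judged sufficient for the primary comparison. At least 20 patients are to be randomized.

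**Conclusion.** The point holds as a minor contradiction in the AE recording rules. Section 8.3.1.1 places a test result where the rest of the protocol requires a sign, symptom or diagnosis, and a normal result is not an AE under Appendix B 1.

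The possible consequence is confined to event counts and SOC/PT rows in descriptive tables. The size of 3.3 to 10 percentage points per affected patient in the row concerned rests on three assumptions: the entry is coded as its own term, each affected patient has one such entry, and the safety set has about 30 to 10 patients per arm. The zero change in patients with any AE assumes that the accompanying symptom or diagnosis is itself recorded as an AE, as the bullet directs.

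**What to change.** Amend Section 8.3.1.1 to say:

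- If the test is positive, the AE term is the diagnosis, COVID-19 infection.
- If the test is negative, the AE term is only the sign, symptom or alternative diagnosis.
- The swab result (positive, negative or not done) goes in a separate eCRF field linked to the AE and is not coded as an AE.

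The 'COVID-19 suspected' entry for untested cases can stay. Query any 'COVID-19 negative' or 'COVID-19 positive' terms already entered, so that they are re-recorded under the same rule.

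The cost is a few lines of protocol text, one added eCRF field, a revised completion guideline and a few queries. Testing, withdrawal and patient care are unchanged.

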8.3.3 Follow-up of adverse events and serious adverse events

After the initial AE/SAE report, the Investigator is required to proactively follow each patient at subsequent visits/contacts. All AEs will be followed until resolution, stabilization, the event is otherwise explained, or the patient is lost to follow-up.

Any AEs that are unresolved at the Follow-up Visit in the study are followed up by the Investigator for as long as medically indicated, but without further recording in the eCRF. AstraZeneca retains the right to request additional information for any patient with ongoing AE(s)/SAE(s) at the EOS, if judged necessary.

8.3.4 Adverse event data collection

The following variables will be collected for each AE:

- Adverse event (verbatim)
- The date when the AE started and stopped
- Maximum intensity grade per National Cancer Institute Common Terminology Criteria for Adverse Events (NCI-CTCAE) Grade version ≥ 5.0
- Whether the AE is serious or not

- Investigator causality rating against the study treatment (yes or no)
- Action taken with regard to study treatment
- Adverse event caused by patient's withdrawal from study
- Outcome

In addition, the following variables will be collected for SAEs:

- Date AE met criteria for SAE
- Date Investigator became aware of SAE
- Adverse event is serious due to
- Date of hospitalization
- Date of discharge
- Probable cause of death
- Date of death
- Autopsy performed
- Causality assessment in relation to study procedure(s)
- Causality assessment to other medication
- Description of AE

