- m Vital signs will include tympanic temperature, systolic and diastolic BP, pulse rate and respiratory rate. Blood pressure should be measured prior to the hemodialysis procedure. For patients on PD, BP should be measured in the morning prior to the patient performing the first exchange of the day. Pulse rate and BP should be measured in triplicate after being comfortably at rest in a seated position with the back and feet supported (ie, by chair back and floor or platform, respectively) quietly for at least 5 minutes.
- n Alanine aminotransferase, AST, ALP, albumin, and TBL.
- o Serum iron, ferritin, TIBC, TSAT, transferrin, soluble transferrin receptor. On Days 1 and 15, blood samples for these assessments will be collected **before** time T0 (ie, **before administration of the single dose of oral iron**). Note that serum iron and TIBC are included in the ferrokinetic study and should not be taken as part of the iron profile as well on Days 1 and 15. There is no need to collect duplicate sample for serum iron and TIBC. The sample collected before the single dose of oral iron is administered can serve for the iron profile as well.
- p Intravenous iron and TRIFERIC® in dialysate should be stopped at the Screening Visit (ie, at Visit 1) and should not be taken after stopping, throughout the Screening and Treatment Periods, but can be started again after the Treatment Period.
- q Must be conducted prior to randomization at Day 1 and prior to the hemodialysis procedures at Days 1 and 15.
- r The blood samples for the ferrokinetic study (serum iron and TIBC) must be taken immediately **before** the single dose of oral iron is administered (ie, immediately before time T0), and then at T1, T2 and T3 after the single dose of oral iron (sample for serum iron only). The window of allowance for the ferrokinetic study blood sampling will be ±3 minutes.
- s Collect from female patients of childbearing potential only.
- t Results for Screening Period assessments for **ALT, AST and TBL must be available before randomization**. Randomization must occur after the ferrokinetic study has completed, ie, after collection of the T3 serum iron sample. Patients will be randomly assigned in 1:1 ratio to either roxadustat or rHuEPO. Study treatment to be administered after randomization at Day 1.

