2. Treatment Period: 2 weeks. Treatment Period procedures will be performed according to the SoA, [Table 1](#) in all randomized patients. For patients who are already on rHuEPO, the start of the Treatment Period (Day 1) should be scheduled to fit into the rHuEPO administration regimen (ie, rHuEPO dosing must occur on the day of the Randomization Visit, Visit 2, Day 1). Patients should be instructed not to take their rHuEPO dose in the morning before they attend the study site for the randomization visit (Visit 2, Day 1).

At Days 1 and 15, a ferrokinetic study will be done in all patients. Immediately **before** time T0 of the ferrokinetic study, a blood sample will be collected to measure baseline serum iron level and TIBC, immediately followed by administration of a defined single dose of oral liquid elemental iron containing FeSO₄ (12.5 mL dose, comprising 100 mg elemental iron). Gastrointestinal iron absorption (serum iron level measured) will then be assessed at 1, 2 and 3 hours **after** the administration of the defined single dose of oral iron (T1, T2 and T3, respectively). The window of allowance for the ferrokinetic study blood sampling will be ± 3 minutes. Patients on HD will have their HD when the ferrokinetic study is completed ie, after the T3 timepoint. For patients on PD, there are no timing restrictions for their PD in relation to the timing of the ferrokinetic study.

On Day 1, after the ferrokinetic study has completed (ie, after collection of the T3 serum iron sample), patients will be randomized in a 1:1 ratio to either rHuEPO treatment or roxadustat treatment. Patients will be centrally randomized by interactive voice response system (IVRS) and stratified by dialysis status (DD versus NDD) and by the following strata: NDD (rHuEPO-users vs rHuEPO-naïve) and DD (PD vs HD). The study treatment (roxadustat or rHuEPO) will be administered at the study site on Day 1, after randomization. On Day 1, patients on HD, or PD can take their study treatment after randomization at any time before, during or after dialysis.

Dosing of roxadustat and rHuEPO should be scheduled to occur on Visit 4 (Day 15). On Day 15, patients randomized to the roxadustat group should take the roxadustat in the morning, at least 6 hours before the ferrokinetic study starts. On Day 15, patients randomized to the rHuEPO group should take the rHuEPO within 1-2 hours before the ferrokinetic study.

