5.2 Exclusion criteria

Medical conditions

- 1 New York Heart Association Class III or IV congestive heart failure (CHF) at screening.
- 2 Acute coronary syndrome, stroke, seizure or a thrombotic/thromboembolic event (eg, deep vein thrombosis or pulmonary embolism) within 12 weeks prior to randomization.
- 3 History of severe, chronic, end-stage, or uncontrolled autoimmune liver disease with ALT > 3 x ULN, or AST > 3 × ULN, or total bilirubin > 1.5 × ULN.
- 4 Known hereditary hematologic disease such as thalassemia, sickle cell anemia, a history of pure red-cell aplasia or other known causes for anemia other than CKD.
- 5 Known and untreated retinal vein occlusion or known and untreated proliferative diabetic retinopathy (risk for retinal vein thrombosis).
- 6 Systolic blood pressure (BP) ≥ 160 mm Hg or diastolic BP ≥ 95 mm Hg (confirmed by repeated measurement), within 2 weeks prior to randomization. Patients may be rescreened once BP is controlled.
- 7 History of prostate cancer, breast cancer, renal cell carcinoma or any other malignancy, except the following: cancers determined to be cured or in remission for ≥ 5 years; curatively resected basal cell or squamous cell skin cancers, cervical cancer in situ, or resected colonic polyps.
- 8 Chronic inflammatory diseases such as rheumatoid arthritis, systemic lupus erythematosus (SLE), ankylosing spondylitis, psoriatic arthritis or active inflammatory bowel disease that is determined to be the principal cause of anemia.
- 9 Known hemosiderosis, hemochromatosis or hypercoagulable condition.
- 10 Any prior organ transplant or a scheduled organ transplantation date.
- 11 Any current condition leading to active significant blood loss.
- 12 Known allergy to the study treatment or any of its ingredients.

- 13 Any medical condition, including active, clinically significant infection, that in the opinion of the Investigator or Sponsor may pose a safety risk to a patient in this study, which may confound safety or efficacy assessment or may interfere with study participation.
- 14 Intolerance of oral iron in the past as defined by stomach upset, nausea, vomiting, or diarrhea.
- 15 Active GI bleed.
- 16 Hospitalizations within the 12 weeks preceding study randomization for GI bleeding or CHF.
- 17 Life expectancy <6 months.
- 18 Patients who are likely to be initiated on dialysis within the next 3 months per Investigator's assessment at the time of screening.
- 19 Previous bowel resection.
- 20 Coeliac disease.

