6 STUDY TREATMENTS

Study treatment is defined as any investigational product(s) (including marketed product comparator and placebo) or medical device(s) intended to be administered to a study participant according to the CSP. Study treatment in this study refers to roxadustat and rHuEPO.

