6.1.3 Additional treatments

All patients will receive the same brand of liquid oral iron containing FeSO₄ to be administered as a single oral (liquid) dose of 12.5 mL (100 mg elemental iron) at Days 1 and 15 for the ferrokinetic study.

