8.3.5 Causality collection

The Investigator will assess causal relationship between study treatment and each AE, and answer 'yes' or 'no' to the question 'Do you consider that there is a reasonable possibility that the event may have been caused by the study treatment?'

For SAEs, causal relationship will also be assessed for other medication and study procedures. Note that for SAEs that could be associated with any study procedure the causal relationship is implied as 'yes'.

A guide to the interpretation of the causality question is found in [Appendix B](#) to the CSP.

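### For non-serious AEs, a date-only onset and a single causality rating cannot identify events caused by the oral iron challenge on Days 1 and 15

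*Protocol*

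**What the plan says.** **Iron challenge.** Section 6.1.3 gives all patients a "single oral (liquid) dose of 12.5 mL (100 mg elemental iron) at Days 1 and 15 for the ferrokinetic study". The schedule of activities also marks the iron dose at the Discontinuation Visit. Exclusion criterion 14 shows which symptoms the protocol associates with oral iron: "Intolerance of oral iron in the past as defined by stomach upset, nausea, vomiting, or diarrhea".

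**Order on Day 1.** Footnote t of the schedule states: "Randomization must occur after the ferrokinetic study has completed, ie, after collection of the T3 serum iron sample". Study drug is first given after randomization, on the same day.

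**Order on Day 15.** Under Section 6.2, roxadustat is taken at least 6 hours, and rHuEPO 1 to 2 hours, before the ferrokinetic study starts.

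**AE variables.** Section 8.3.4 lists "The date when the AE started and stopped" and one yes/no causality rating against study treatment. Section 6 defines the term: "Study treatment in this study refers to roxadustat and rHuEPO". The wider question is kept for serious events in Section 8.3.5: "For SAEs, causal relationship will also be assessed for other medication and study procedures".

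**Reporting.** AEs are collected from consent onwards (Section 8.3.2). Section 9.4.4 plans: "Adverse events (and also separately SAEs) will be summarized by study treatment group by incidence summaries". It states no restriction by onset time or causality.

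**The concern.** The iron challenge is a study procedure with recognised gastrointestinal effects, and on Days 1 and 15 it shares a calendar date with a scheduled study-drug dose. On Day 1 it comes before the patient has been assigned to either arm. An upset stomach between the iron dose (T0) and the last sample (T3) cannot be an effect of assigned treatment, yet it carries the same date as the first dose.

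Gastrointestinal upset would mostly be non-serious, and that is the class of event for which the protocol does not ask about other medication or procedures. AE incidence is a stated safety endpoint, so at stake is whether the tables for two small arms can be read as describing the study drugs.

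**Working it through.** The plan states no figure on this point. The check sets the sections side by side and then adds an illustration on assumed rates.

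**Step 1. Can a non-serious Day 1 event be placed before or after the first dose?** The sequence is iron at T0, samples to T3, randomization, first dose, all on one date. The iron and sample clock times go into the eCRF (Section 8.1.1). The AE variables in Section 8.3.4 hold a date only. With no onset time, the recorded iron and sample times have nothing to be compared with. The answer is no.

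**Step 2. Can the causality rating do this instead?** Only in part. The investigator may answer no for study treatment. That answer does not say whether the event began before the dose. It also does not remove the event from the Section 9.4.4 tables as the protocol describes them, because they are not restricted by causality.

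**Step 3. Can a non-serious Day 15 event be identified as iron-related?** No. The record can show that it was unrelated to study treatment, but there is no item for iron, other medication or procedures. An onset time alone would not change its place in the tables, because it starts after study drug has begun and is on-treatment at any hour.

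**Step 4. How large could the effect be?** The protocol gives no event rate for oral iron. Assume a probability q of an iron-caused event per dose, equal and independent across the two doses. The probability of at least one iron event is 1 − (1 − q)². With 1:1 allocation, the minimum of 20 and the maximum of 60 randomized patients give 10 and 30 per arm.

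| Assumed q | 1 − (1 − q)² | Expected patients, 10 per arm | Expected patients, 30 per arm |
|---|---|---|---|
| 2% | 4.0% | 0.4 | 1.2 |
| 5% | 9.8% | 1.0 | 2.9 |
| 10% | 19.0% | 1.9 | 5.7 |
| 20% | 36.0% | 3.6 | 10.8 |

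Let b be the assumed proportion of patients with some other AE, independent of iron events. Crude incidence then rises by (1 − b) × [1 − (1 − q)²]:
- at q = 2%, b = 30%: 0.7 × 0.0396 = 2.8 percentage points;
- at q = 20%, b = 10%: 0.9 × 0.36 = 32.4 percentage points.

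**Step 5. How much of this could be moved out of the on-treatment tables?** Only the Day 1 events that start before the first dose. Their expected number per arm is at most n × q: 10 × 0.02 = 0.2 to 10 × 0.20 = 2.0 patients at 10 per arm, and 30 × 0.02 = 0.6 to 30 × 0.20 = 6.0 at 30 per arm. The rest is a matter of attribution.

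**Step 6. Does it differ between arms?** Both arms take the same dose on the same days, and the Day 1 dose precedes randomization. With the same q in both arms, both rates rise by a similar amount.

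**The case against.** **Investigators can answer no.** The causality question asks about a reasonable possibility for study treatment. Appendix B 8 asks whether the patient had actually received the drug and points to other drugs as an alternative cause. For an event between T0 and T3 on Day 1 the proper answer is no, and staff are drawing blood hourly in that window. This stands. A reader might infer that iron-caused events are charged to roxadustat or rHuEPO, and the protocol does not support that. What is missing is a way to record that iron was the cause, and a way to place the event before the first dose.

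**No bias between arms follows.** A reader might also infer that, in an open-label trial, iron events would be blamed more readily on the oral drug and so set off the 24-hour roxadustat reaction reports of Section 8.3.2. No section supports that step. On Day 15 rHuEPO is given closer in time to the iron than roxadustat, and the report is due only if the investigator judges roxadustat a reasonable cause.

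**Serious events are covered.** They carry causality ratings for other medication and for study procedures, so the gap is confined to non-serious events.

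**The impact is limited.** Safety analysis is descriptive, and patients with past oral iron intolerance are excluded. Both points stand and lower the priority.

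**A pre-treatment rule may be in the SAP.** The SAP is not shown, so the absence of such a rule from the protocol is no fault. But no rule written later can recover an onset time that was never collected, and Section 8.3.4 is where the collected variables are set.

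**Conclusion.** The point holds as a narrow gap in data collection. For non-serious AEs, the variables in Section 8.3.4 cannot separate a Day 1 event caused by iron before randomization from one after the first dose, and they cannot identify an iron-related event on Day 15. Crude AE rates can be inflated and attribution is lost, in both arms alike.

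The size is unknown because the protocol gives no iron event rate. Over assumed rates of 2% to 20% per dose, and other-AE incidence of 10% to 30%, crude incidence would rise by about 3 to 32 percentage points per arm. Those figures assume independent doses and equal rates in both arms, and they are illustrative. Exclusion of patients with known intolerance argues for the lower part of the range, though the documents do not say how far.

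No between-arm bias is shown, and the primary endpoint, which rests on serum iron, is unaffected. Priority: optional improvement.

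**What to change.** - **Section 8.3.4:** for AEs starting on Day 1, record whether onset was before or after the first study dose, or record the onset time. For AEs starting on any iron day (Day 1, Day 15, Discontinuation Visit), record whether onset was before or after the iron dose.
- **Section 8.3.5:** extend the existing SAE causality items on other medication and study procedures to non-serious AEs on iron days, and name the iron challenge as an option.
- **Section 9.4.4 or the SAP:** report Day 1 events that start before the first study dose as pre-treatment. Day 15 events remain on-treatment; for those the gain is the causality item.

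The cost is a few eCRF fields, a sentence in each section, and slightly more AE data entry on the iron-challenge visit days. Iron and sample times are already captured. No dose, schedule or clinical rule changes.
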